3.7.5 Vital Signs

Vital signs measurements include pulse rate, temperature, systolic blood pressure, and diastolic blood pressure. Measures at baseline and changes from baseline to post baseline visit will be summarized. The number and percentage of subjects with abnormal blood pressure will be summarized.

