9.2. Vital signs

Vital signs will be measured by a qualified staff member at Visit 1, Visit 2 prior to randomization, Visit 4 (cohort 1 ONLY) prior to treatment and at Visit 8. The following items will be measured:

- Body temperature
- Pulse rate
- Respiration rate

- Blood pressure (systolic and diastolic) after the subject sits quietly for at least 5 minutes
- Height (at Visit 1 only)
- Weight (at Visit 1 only).

Any measure that is, in the opinion of the investigator, abnormal AND clinically relevant (CR) must be recorded as history if found prior to the first study medication treatment or as an AE if found after the first study medication treatment begins (Section 10.1).

A systolic blood pressure >140mm Hg or a diastolic blood pressure >90mm Hg is considered abnormal and therefore must be defined as CR or not clinically relevant (NCR) on the CRFs.

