12.4. Statistical Analysis of Safety Data

Safety analyses will include descriptive statistics calculated on the safety parameters using the ITT population. The proportion of subjects with treatment-emergent adverse events will be tabulated and presented by study treatment group and Medical Dictionary for Regulatory Activities (MedDRA) System Organ Class. Vital signs, LSR scores and clinically relevant abnormal laboratory results will also be tabulated and presented.

Data from all treated subjects will be presented and summarized. Safety summaries by study treatment group will include listings by study medication of adverse events incidences within each MedDRA System Organ Class, and changes from pre-treatment values in vital signs. Adverse event summaries will be presented showing the proportion of subjects experiencing adverse events, both overall and by MedDRA System Organ Class.

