2.4.3.4 Vital Signs

Vital signs will be measured by a qualified staff member at Visit 1, Visit 2 prior to randomization, Visit 4 (cohort 1 ONLY) prior to treatment and at Visit 8. The following items will be measured:

- Body temperature
- Pulse rate
- Respiration rate
- Blood pressure (systolic and diastolic) after the subject sits quietly for at least 5 minutes
- Height (at Visit 1 only)
- Weight (at Visit 1 only)

Any measure that is, in the opinion of the investigator, abnormal AND clinically significant (CS) must be recorded as history if found prior to the first study medication treatment or as an AE if found after the first study medication treatment begins.

A systolic blood pressure >140mm Hg or a diastolic blood pressure >90mm Hg is considered abnormal and therefore must be defined as CS or non-clinically significant (NCS) on the Case Report Forms (CRFs).

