4 CHANGES TO PLANNED ANALYSES

After communications with the FDA, the sponsor is no longer persuing a separate indication for in patients with DPN. Therefore, an abbreviated report will be produced for A-101-DPN-201. This abbreviated report will contain all the safety of a full report, but only the primary and key secondary efficacy analyses will be reported. As a result, the following descriptive statistics mentioned in the protocol will not be produced:

- Number and percentage of lesions by PLA score categories (clear, near-clear, small, and large): overall, separately for face or neck target lesions, separately for subjects with FST 5 and 6;
- Summary statistics on PLA score (mean of all lesions): overall and separately for subjects with FST 5 and 6;
- Summary statistics on percentage of lesions that are clear (PLA=0): overall, separately for face or neck target lesions, separately for subjects with FST 5 and 6;
- Summary statistics on percentage of lesions that are clear or near clear (PLA=0 or 1): overall, separately for face or neck target lesions, separately for subjects with FST 5 and 6;
- Number and percentage of lesions by location (face, or neck): overall and separately for subjects with FST 5 and 6.

Furthermore, the following hypothesis tests will not be performed:

- Change in percentage of lesions that are clear (PLA=0) from baseline evaluation to the last evaluation of the lesions ANCOVA model;
- Change in percent of lesions that are clear (PLA=0) or near-clear (PLA=1) from baseline evaluation to the last evaluation of the lesions ANCOVA model;
- Change in longest lesion diameter from baseline to the last lesion measurement ANCOVA model;

The protocol also states that efficacy summaries may be presented for the intent-to-treat (ITT) population using LOCF to impute missing data. The primary endpoint will be summarized and analyzed for the ITT population using LOCF to impute missing data, but none of the other efficacy endpoints will be summarized or analyzed for the ITT population.

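### SAP 3.7.5 leaves out respiration rate without declaring it, and its abnormal blood pressure count cannot separate newly abnormal subjects from those already abnormal before treatment

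*SAP*

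**What the plan says.** **Collection.** Protocol 9.2 and SAP 2.4.3.4 have the same list: temperature, pulse, "Respiration rate" and blood pressure, plus height and weight at Visit 1 only. Readings are taken at Visit 1, at Visit 2 before treatment, and then at "Visit 4 (cohort 1 ONLY) prior to treatment and at Visit 8".

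**Threshold.** SAP 2.4.3.4 states: "A systolic blood pressure >140mm Hg or a diastolic blood pressure >90mm Hg is considered abnormal and therefore must be defined as CS", or else as not clinically significant (NCS), on the case report form. Protocol 9.2 sets the same limits and labels the call CR/NCR. The limits are absolute and do not refer to the subject's baseline.

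**Analysis.** SAP 3.7.5 states: "Vital signs measurements include pulse rate, temperature, systolic blood pressure, and diastolic blood pressure". It continues: "Measures at baseline and changes from baseline to post baseline visit will be summarized". It ends: "The number and percentage of subjects with abnormal blood pressure will be summarized". It names no visit, baseline condition or shift for that last output.

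**Commitments.** Protocol 12.4 plans "changes from pre-treatment values in vital signs" and excepts no measure. SAP Section 4 states: "This abbreviated report will contain all the safety of a full report". The omissions it declares are all lesion or efficacy outputs.

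**The concern.** There are two gaps in a safety output, and safety is part of the primary objective.

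First, a measure that the protocol collects and promises to analyse drops out of the SAP. The section that records changes from the protocol does not mention it.

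Second, the only categorical vital-sign output does not answer the question a safety reader asks, which is how many subjects went from normal to abnormal blood pressure after treatment. Protocol 5.1 and 5.2 set no blood pressure limit for entry, so subjects above the threshold at Visit 1 or 2 can enrol and can appear in the count. A stable group of already-abnormal subjects and a set of new cases could give the same number.

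**Working it through.** The documents give no blood pressure rate, so there is no planned figure to reproduce. The check compares sections and does day arithmetic.

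**1. Respiration rate**

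- Measured repeatedly (Protocol 9.2, SAP 2.4.3.4): temperature, pulse, respiration rate, systolic pressure, diastolic pressure = 5.
- Listed for summary (SAP 3.7.5): pulse, temperature, systolic pressure, diastolic pressure = 4.
- Missing: 5 − 4 = 1, respiration rate. It is not among the omissions in SAP Section 4.

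**2. What the count can show**

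Take the reading most favourable to the SAP: the count is shown at each nominal visit (SAP 3.1), baseline included. Let *n* be the subjects measured at both times, *b* the number abnormal at baseline, *v* the number abnormal at Visit 8, and *k* the number abnormal at both.

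- New cases = *v* − *k*, where max(0, *b* + *v* − *n*) ≤ *k* ≤ min(*b*, *v*).
- Illustration in Arm A, where 1:2 allocation of 24 gives 24 × 1/3 = 8 subjects, with *b* = *v* = 3: the lower limit is max(0, 3 + 3 − 8) = 0 and the upper limit is min(3, 3) = 3.
- New cases therefore lie anywhere from 3 − 3 = 0 to 3 − 0 = 3.

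The two margins do not determine the answer; the cross-tabulation does.

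**3. Whether the change summaries fill the gap**

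Three subjects rising and three falling by the same amount give a mean change of zero, as does no change in anyone. The standard deviation and range of the changes would hint at movement, but they do not show who crossed the threshold or in which direction.

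**4. Whether the adverse event tables fill the gap**

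| Item | Source | Days |
|---|---|---|
| Treatment-emergent window ends, Cohort 1 | Visit 4 (Day 22, +4) plus 30 (SAP 3.7.3) | 22 + 30 = 52 to 26 + 30 = 56 |
| Treatment-emergent window ends, Cohort 2 | Visit 5 (Day 29, +4) plus 30 | 29 + 30 = 59 to 33 + 30 = 63 |
| Adverse event collection ends | Visit 6, Day 50 ± 7 (Protocol 10.1.3, SAP 2.4.3.2) | 43 to 57 |
| Visit 8 reading | Day 106 ± 7 | 99 to 113 |

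The windows assume that the last scheduled treatment is given; without it they close earlier. The schedule footnotes end most safety reporting earlier still, at Visit 5. The earliest Visit 8 reading comes 99 − 63 = 36 days after the latest end of the treatment-emergent window and 99 − 57 = 42 days after the latest Visit 6.

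Protocol 9.2 sends any clinically significant abnormal value found after first treatment to the adverse event form. Even if a site did this for a Visit 8 reading, the event would fall outside the treatment-emergent definition. In Cohort 2 that is the only post-baseline reading. In Cohort 1 the Visit 4 reading (Day 22 to 26) is inside the window, so a clinically significant value there does reach the tables.

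**The case against.** The strongest defence is that the SAP is silent rather than wrong. It does not say that baseline is to be ignored. SAP 3.1 defines baseline and uses nominal visits, so a by-visit table with a baseline row is a natural reading. Systolic and diastolic pressure also get baseline and change summaries, so a high abnormal rate with no overall change would be visible as such. This stands, and it confines the point to one line of the output. It does not remove it, because step 2 of the working already assumes that favourable reading.

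A reader might infer more than the documents support:

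- *That the investigator's significance call is discarded.* It is not. Clinically significant readings go to medical history if found before treatment and to adverse events if found after. Medical history is tabulated (SAP 3.4), as are treatment-emergent events (SAP 3.7.3). The gap is narrower: Visit 8 readings fall outside the windows, and 3.7.5 does not show the call beside the count.
- *That Cohort 1 will look worse because it has one more reading.* This needs a count over any visit, which the SAP does not state, and a comparison between cohorts, which it does not plan. The planned comparisons are within Cohort 2, where both arms share one schedule.
- *That the table would then show an effect of treatment.* It would not. Every arm receives A-101, and Visit 8 comes 106 − 29 = 77 days after a Day 29 application. The table would identify new abnormal readings, not their cause.

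It is also fair to say that this is one descriptive line in a 36-subject study of a topical product.

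**Conclusion.** Both points hold, and both are minor. The omission of respiration rate rests on the text alone. The blood pressure point rests on the SAP's silence about baseline, together with a fixed threshold and no entry limit on blood pressure. It does not depend on any assumed rate.

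How many subjects will be abnormal before treatment cannot be sized from the documents, and a reader should not infer a proportion. Nor do the documents support calling these subjects diseased: they define an abnormal reading, not a diagnosis.

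What can be said is that the arms are small. If the planned numbers are treated, one subject is 1/8 = 12.5% of Arm A and 1/16 = 6.25% of Arm B, so whether an abnormal reading is new or pre-existing matters to how each percentage is read. No efficacy result is affected.

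**What to change.** In SAP 3.7.5:

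1. Add respiration rate to the listed measures, so that it gets the same baseline and change summaries.
2. Replace the sentence on abnormal blood pressure with wording such as: *For each arm, blood pressure category (systolic >140 or diastolic >90 mm Hg, versus neither) will be presented as a shift table from baseline, as defined in Section 3.1, to Visit 8, and for Cohort 1 also to Visit 4. The number and percentage of subjects normal at baseline and abnormal afterwards will be given, with the CS/NCS call shown.*

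Using the Section 3.1 baseline (last value before first treatment) rather than naming Visit 2 covers a missing Visit 2 reading. Shift tables are already planned for local skin reactions in SAP 3.7.2, so the format is not new.

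The cost is one small descriptive table and one extra variable, from data already collected. No visit, procedure or clinical rule changes.

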3.8 INTERIM ANALYSES

There is no interim analyses planned for the study.

4 CHANGES TO PLANNED ANALYSES

After communications with the FDA, the sponsor is no longer persuing a separate indication for in patients with DPN. Therefore, an abbreviated report will be produced for A-101-DPN-201. This abbreviated report will contain all the safety of a full report, but only the primary and key secondary efficacy analyses will be reported. As a result, the following descriptive statistics mentioned in the protocol will not be produced:

- Number and percentage of lesions by PLA score categories (clear, near-clear, small, and large): overall, separately for face or neck target lesions, separately for subjects with FST 5 and 6;
- Summary statistics on PLA score (mean of all lesions): overall and separately for subjects with FST 5 and 6;
- Summary statistics on percentage of lesions that are clear (PLA=0): overall, separately for face or neck target lesions, separately for subjects with FST 5 and 6;
- Summary statistics on percentage of lesions that are clear or near clear (PLA=0 or 1): overall, separately for face or neck target lesions, separately for subjects with FST 5 and 6;
- Number and percentage of lesions by location (face, or neck): overall and separately for subjects with FST 5 and 6.

Furthermore, the following hypothesis tests will not be performed:

- Change in percentage of lesions that are clear (PLA=0) from baseline evaluation to the last evaluation of the lesions ANCOVA model;
- Change in percent of lesions that are clear (PLA=0) or near-clear (PLA=1) from baseline evaluation to the last evaluation of the lesions ANCOVA model;
- Change in longest lesion diameter from baseline to the last lesion measurement ANCOVA model;

The protocol also states that efficacy summaries may be presented for the intent-to-treat (ITT) population using LOCF to impute missing data. The primary endpoint will be summarized and analyzed for the ITT population using LOCF to impute missing data, but none of the other efficacy endpoints will be summarized or analyzed for the ITT population.

Lastly, the ANCOVA model described in the protocol for the primary endpoint has been replaced with a repeated measures mixed model in order to capture changes over time in the primary efficacy endpoint and account for within subject correlation in the repeated measures over time. The number of treated lesions is also being added as a covariate in the primary efficacy model and the logistic regression model for responders which was not considered in the protocol.
